### **9.1.2.2. Analysis Method**

Time to worsening will be estimated using Kaplan-Meier methods. The hazard ratio for daratumumab relative to active monitoring and its associated 95% confidence interval (CI) will be calculated based on the stratified Cox proportional hazards model by the stratification factor at the randomization. Death due to disease progression will be considered as worsening. Subjects who have not met the definition of worsening will be censored at the last PRO assessment. Subjects without baseline assessment or post-baseline assessment will be censored at date of randomization.

Time to improvement will be summarized using descriptive statistics such as mean, standard deviation (SD), median and range.

**ATTACHMENT 1: ADDITIONAL EXPLORATORY ANALYSIS TO SUPPORT HEMAR****1. DEFINITION OF SUBGROUPS**

Subgroup analyses will be performed for the ITT population, pre-defined subgroups as defined in section 2.4, and for the following subgroups:

- For subjects who reached CR/sCR as their best response
- For subjects who reached VGPR as their best response
- For subjects who reached PR as their best response
- For subjects who reached PD as their best response
- For subjects who achieved a PR or better
- For subjects who achieved MRD negativity ( $10^{-4}$ ,  $10^{-5}$  and  $10^{-6}$ )
- Baseline ECOG performance status (0 or 1)
- Baseline risk factors (grouped) for progression to MM ( $<3$  vs  $\geq 3$ )
- Baseline risk factors (Stand-alone) for progression to MM:
  - Serum M protein  $\geq 30\text{g/L}$
  - IgA SMM
  - Immunoparesis with reduction of 2 uninvolved immunoglobulin isotypes (only IgA, IgM and IgG)
  - Serum involved : uninvolved FLC ratio  $\geq 8$  and  $<100$
  - Clonal BMPCs  $>50\%$  to  $<60\%$  with measurable disease
  - Serum M protein  $> 2\text{ g/dL}$
  - I/U FLC ratio  $> 20$
  - BMPC  $> 20\%$

Subgroup analyses will be performed if data warrants.

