## 5.2. Primary Efficacy Endpoint(s)

### 5.2.1. Definition

The primary endpoint of this study is PFS as assessed by the independent review committee (IRC), defined as the duration from the date of randomization to either progression to multiple myeloma, according to the IMWG diagnostic criteria for MM, or death due to any cause, whichever occurs first. Progression evaluations for the primary endpoint/final analysis were based on IRC review, in a blinded fashion, to objectively and consistently implement the IMWG diagnostic criteria for MM. Data from the central laboratory, local clonal plasma cell assessment and images performed at the study site (or designated facility) assessed by independent radiological review were provided to IRC for progressive disease identification. Subjects who start anti-cancer therapies for multiple myeloma without disease progression will be censored at the last disease assessment before the start of subsequent therapies. Subjects who withdraw consent from the study before disease progression will be censored at the last disease assessment before withdrawal of consent to study. Subjects who are lost to follow-up will be censored at the last disease assessment before the subjects were lost to follow-up. Subjects who have not progressed and are still alive at the clinical cut-off date for analysis will be censored at the last disease assessment. Subjects without any post-baseline disease assessment will be censored at randomization.

Determination of dates of PFS event and dates for censoring is summarized in [Table 4](#) as follows.

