## 5.3.5. Progression-free Survival on First-line Therapy for MM

### 5.3.5.1. Definition

Progression-free survival on first-line therapy (PFS2) is defined as the time from randomization to progression on first-line therapy or death, whichever comes first. Disease progression will be based on investigator assessment. Any deaths are considered as PFS2 events. Subjects who start first-line therapy without disease progression on study treatment will be censored at the last disease assessment on or before starting first-line therapy. Subjects who start first-line therapy after progression on study treatment, are still alive and not yet progress on first-line therapy, will be censored at the last date of follow-up or the day before the start date of 2nd line of next therapy, whichever comes first. Subjects without any post-baseline follow-up will be censored at the randomization. Subjects who were already diagnosed multiple myeloma per baseline central imaging review will be censored at randomization.

Determination of dates of PFS2 event and dates for censoring is summarized in [Table 5](#) as follows.

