## **5.3.6. Overall Survival**

### **5.3.6.1. Definition**

Overall survival is measured from the date of randomization to the date of death due to any cause. Subjects who are lost to follow-up will be censored at the last known alive date. Subjects who died after consent withdrawal will be considered as having an OS event. Subjects who are still alive at the clinical cut-off date for the analysis or the survival status is unknown will be censored at the last known alive date. The date of last known alive will be determined by the maximum collection/assessment date from among selected data domains within the clinical database.

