## 8. BIOMARKERS

Biomarker studies are designed to evaluate if there are any differences in depth of response, cytogenetic risk factors and immune-phenotypes in high risk SMM patients. Samples for biomarker evaluations will be collected as specified in the protocol Time and Events Schedule for bone marrow aspirate samples and whole blood samples.

With the emergence of highly effective drug regimens for multiple myeloma that effectively eliminate malignant plasma cells, the utility of assessing minimal residual disease (MRD) has gained greater importance in determining the depth of response to therapy. For this study, three threshold values,  $10^{-4}$ ,  $10^{-5}$  and  $10^{-6}$ , may be used to evaluate MRD negativity status and its predictive value for PFS and OS. The MRD negative rate will be calculated for the Daratumumab treatment group and the corresponding 95% exact CI will be provided.

A portion of the bone marrow aspirate samples collected, as specified in the Time and Events Schedule, will be utilized for translocation/mutation/genomic analysis (DNA/RNA) to assess whether specific molecular subgroups are responsive to daratumumab treatment. The high risk molecular subgroup is defined as subjects who have either del17p, t(4;14), t(14; 16), amp1q or a combination of these. This definition of high risk may evolve with emerging data from the scientific community. The standard-risk molecular subgroup includes subjects who had molecular test results by bone marrow aspirate, but do not meet molecular high-risk criteria. Analyses will evaluate ORR, PFS and OS as it relates to risk within each arm to see if they have similar outcomes to standard risk patients.

Biomarker studies are designed to identify markers predictive of response (or resistance) to daratumumab. Exploratory analyses, stratified by clinical covariates or molecular subgroups, may

be performed using the appropriate statistical methods (eg, parametric or non-parametric, univariate or multivariate, analysis of variance, or survival analysis, depending on the endpoint).

Subjects may be grouped by cohort, dose schedule, or clinical response. As this is an open-label study with an active monitoring control arm, statistical analyses will be done to aid in the understanding of the results.

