**2. ENDPOINTS FOR SUBGROUP ANALYZES**

As described in Sections 5.2 (Primary Efficacy Endpoints), 5.3 (Secondary Endpoints) and 9.1 (Patient-Reported Outcomes), the following endpoints will be evaluated by subgroups as defined in Section 1, Appendix:

- PFS
- Time to Biochemical or SLiM-CRAB progression
- ORR
- Time to first-line treatment for MM
- PFS2
- OS
- Duration of response
- Time to Response
- EORTC QLQ-C30, EORTC QLQ-MY20, EQ-5D-5L (Section 9.1.1.1)
- PRO: Time to worsening/improvement (Section 9.1.1.2)
- Time to progression
- Incidence of MM with adverse prognostic features

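### SAP Attachment 1 times PFS, PFS2 and OS from randomization in subgroups defined by later response or MRD status, so responder curves contain guaranteed event-free time

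*SAP*

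**What the plan says.** SAP Attachment 1, Definition of Subgroups, puts true baseline subgroups (ECOG status, risk factors) in one list with subgroups known only after randomization. The latter are best response of CR/sCR ("For subjects who reached CR/sCR as their best response"), VGPR, PR or PD; "For subjects who achieved a PR or better"; and "For subjects who achieved MRD negativity" at three thresholds. The next section, on endpoints for the subgroup analyses, refers back to SAP Sections 5.2 and 5.3 and states that "the following endpoints will be evaluated by subgroups as defined in Section 1, Appendix". The list includes PFS, biochemical or SLiM-CRAB (BOD) progression, time to first-line treatment for MM, PFS2 and OS.

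The clocks in those sections start at randomization:

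- PFS (Section 5.2.1): "defined as the duration from the date of randomization to either progression to multiple myeloma" or death.
- PFS2 (Section 5.3.5.1): "is defined as the time from randomization to progression on first-line therapy or death, whichever comes first".
- OS (Section 5.3.6.1): "Overall survival is measured from the date of randomization to the date of death due to any cause".
- BOD progression (Section 5.3.1.1) and time to first-line treatment (Section 5.3.4.1) have the same origin.

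The analysis method in Section 5.2.3, which the secondary time-to-event endpoints follow, is Kaplan-Meier by arm, a stratified log-rank test, and a stratified Cox model whose only covariate is treatment. The attachment is titled exploratory, and its subgroup analyses are conditional on the data supporting them.

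**The concern.** Membership of a responder or MRD-negative subgroup is earned during follow-up. A subject who progresses, dies or starts new therapy before responding cannot join, so the time from randomization to response is event-free by construction. Counting that time in the subgroup's curve makes the outcome look better than it is (immortal time). The group with PD as best response has the mirror problem: poor PFS is built in.

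If the Section 5.2.3 method is taken literally, the attachment also produces a daratumumab-versus-monitoring hazard ratio inside each response group. That conditions on something treatment influences, so the two arms within a group are no longer comparable through randomization.

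Neither document gives a response landmark, a time-dependent covariate, a reset of the clock or a caveat for these analyses. The landmark PFS rate in Section 5.2.3 is a Kaplan-Meier rate by arm at fixed times and does not address response status. At stake is misreading of prespecified outputs, not the trial's main conclusion.

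**Working it through.** The plan gives no figure on this point to reproduce. The argument is structural, and the numbers below only show its size.

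**1. What a subject must do to enter a responder group.** Response categories need two consecutive assessments before any new therapy (Protocol Table 8). Disease evaluation is every 12 weeks (SAP Section 1.2). MRD is monitored in subjects who attain CR/sCR (SAP Section 1.2), with some VGPR cases added when assay interference is suspected (Protocol Section 9.4). MRD negativity therefore generally comes later still.

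**2. Event-free time implied by the visit schedule.** On scheduled visits alone, the earliest confirmed response is at week 24, or 168 / 30.44 = 5.5 months. With exponential PFS at the design medians (SAP Section 1.4), the chance of an event before then is:

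- daratumumab: 1 − 2^(−5.5/48) = 7.6%
- active monitoring: 1 − 2^(−5.5/30) = 11.9%

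None of these subjects can appear in a responder curve. Protocol Table 8 lets the two assessments fall at any time, so an unscheduled repeat could shorten the interval. Later responses lengthen it.

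**3. Size if response groups were compared with each other.** Null simulation in the daratumumab arm, 400,000 subjects per scenario, with response independent of the event (true HR 1.00).

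- From the documents: median PFS 48, PFS2 96 and OS 125 months. Follow-up is uniform over 24–48 months for PFS (24-month accrual plus 24 months) and 72–96 months for PFS2 and OS (end of study at about 8 years).
- Assumed, because the documents do not give them for this trial: 60% or 10% eventual responders, and lognormal time to response with log-scale SD 0.6 and the medians shown.

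Cox HR for ever-responders versus the rest, timed from randomization:

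| Eventual responders | Median time to response (months) | PFS | PFS2 | OS |
|---|---|---|---|---|
| 60% | 2 | 0.81 | 0.91 | 0.92 |
| 60% | 6 | 0.59 | 0.77 | 0.78 |
| 60% | 12 | 0.41 | 0.62 | 0.63 |
| 10% | 6 | 0.76 | 0.88 | 0.91 |
| 10% | 12 | 0.59 | 0.78 | 0.80 |
| 10% | 18 | 0.49 | 0.69 | 0.70 |
| 10% | 24 | 0.42 | 0.62 | 0.62 |

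On the same data, a 12-month landmark gives 0.98 to 1.03 and a time-dependent covariate gives 0.99 to 1.02.

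**4. What a landmark costs.** With median PFS 48 months and no censoring before 24 months, a 12-month landmark keeps 2^(−12/48) = 84% of daratumumab subjects for PFS. A 36-month landmark keeps 2^(−36/48) × 0.5 = 0.595 × 0.5 = 30%; the 0.5 is the share with more than 36 months of follow-up.

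Early landmarks misclassify late responders. Under the assumed lognormal, and before allowing for events and censoring, the share of eventual responders who respond after 12 months is 1 − Φ(ln(12/18)/0.6) = 75% for a median of 18 months, and 1 − Φ(ln(12/24)/0.6) = 88% for a median of 24 months.

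**The case against.** The strongest objection concerns which contrast is planned. A reader might infer that the SAP will report responder-versus-non-responder hazard ratios as extreme as 0.4. The text does not support that. The only hazard ratio carried over from Section 5.2.3 is for treatment, and the attachment defines no general non-responder group. For the literal contrast, arm against arm within responders, a simulation with response independent of PFS and equally timed in both arms gave 1.01–1.03 under the null and 0.59–0.61 when the true HR was 0.625. Immortal time then affects both arms alike and distorts the ratio little.

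This stands as far as it goes. It does not clear the curves, which still contain the guaranteed time. It also rests on equal response in the two arms, which cannot be assumed when Arm A receives no disease-specific treatment (Protocol Section 3.1). The selection effect when responders differ between arms has not been quantified.

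The size is also uncertain. The only response-time figure in the documents is a 4-week median, range 4 to 8 weeks, in relapsed or refractory myeloma (Protocol Section 1.1). The phase 2 SMM study's long-intense arm had an ORR of 56.1% but a CR rate of 2.4% at an early interim (Protocol Table 4). Fast responses would put the distortion at the mild end of the table.

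Two further inferences should not be drawn. SAP Section 8 says MRD thresholds "may be used to evaluate MRD negativity status and its predictive value for PFS and OS", but it states no time origin or model, so it is not an instance of this problem. And although the attachment is meant to support HEMAR, neither document says how the curves will be used in economic work.

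Finally, not every listed endpoint is affected. Duration of response starts at response, and time to response is already confined to responders.

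**Conclusion.** The point holds for the response- and MRD-defined subgroups of Attachment 1. Followed as written, the plan gives responder curves with guaranteed event-free time, a PD subgroup selected for progression without response, and between-arm hazard ratios open to post-randomization selection. These conclusions follow from the text and need no assumption about response timing.

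The range of about 0.4 to 0.9 applies only if response groups are compared with each other, and it rests on the assumed response rates and times. In every scenario run, the error favoured responders.

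A reader might take this as a threat to the trial's result, but it is not one. The analyses are exploratory and conditional, and they lie outside the PFS, ORR, PFS2 and OS testing sequence in SAP Section 5.1.1. The primary analysis and type I error are unaffected.

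**What to change.** In Attachment 1, separate the subgroups defined by best response or MRD status from the baseline subgroups, and leave the baseline ones as they are. For the response- and MRD-defined groups:

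- Replace the analyses of PFS, BOD progression, time to first-line treatment, PFS2 and OS from randomization with a model that has response or MRD status as a time-dependent covariate. This is preferable for CR and MRD negativity, which may come late.
- Alternatively, prespecify landmark times, classify by status reached at the landmark, include only subjects still event-free and under follow-up, and time from the landmark.
- Report no between-arm hazard ratio within these groups.
- Omit ORR within the PR-or-better group, where it is 100% by construction.

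The cost is a wording change and modest programming. A landmark drops subjects with earlier events or censoring and counts later responders as non-responders. The time-dependent model avoids both losses, but it does not give a simple Kaplan-Meier curve for a fixed group.

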**2. ENDPOINTS FOR SUBGROUP ANALYZES**

As described in Sections 5.2 (Primary Efficacy Endpoints), 5.3 (Secondary Endpoints) and 9.1 (Patient-Reported Outcomes), the following endpoints will be evaluated by subgroups as defined in Section 1, Appendix:

- PFS
- Time to Biochemical or SLiM-CRAB progression
- ORR
- Time to first-line treatment for MM
- PFS2
- OS
- Duration of response
- Time to Response
- EORTC QLQ-C30, EORTC QLQ-MY20, EQ-5D-5L (Section 9.1.1.1)
- PRO: Time to worsening/improvement (Section 9.1.1.2)
- Time to progression
- Incidence of MM with adverse prognostic features

## 2. EXPOSURE ADJUSTED INCIDENCE RATES (EAIR)

### 2.1. Restriction on the first event

The analysis restricts on the occurrence of the first event per patient and ignores the existence of later (multiple) events as these cannot be assumed to occur independent of previous events (e.g.: patients suffering from infections may have in general a higher risk of having other complications and may even have a higher risk of getting other infections). The occurrence of multiple events is subject to another analysis considering the absolute number of adverse events per patient.

For these reasons the EAIR should be interpreted as '*rate until the first event occurs*'. Rates estimated from several patients can be averaged on the level of a preferred term (PT), of a system organ class (SOC), or on a global level (see below).

The interpretation of EAIRs is simple and consistent on the preferred-term level only, and can be expressed as "*Average number of TEAEs per preferred-term emerging per person-month of exposure*".

The aforementioned considerations apply in the same way to EAIRs estimated on the global level: when EAIRs are collapsed into the global estimate (first analyses), the estimate can be interpreted as the "*Average number of TEAEs emerging per person-month and PT*", because estimation has been performed on a '*per PT*'-basis (per *average* or *typical* PT among all PTs).

Comparing EAIRs on the level of the SOC or on the global level involves data destruction because a patient's information is reduced to the first TEAE only (and possibly to a TEAE of marginal relevance among many TEAEs with higher clinical relevance).

The EAIR analysis focuses on the 'speed' by which TEAEs emerge. The analysis restricts on the first event of a patient because independence of TEAEs cannot be assumed. The necessity to restrict on the first event entails considerable data destruction when deriving SOC-specific EAIRs or the EAIR on a global level. To overcome this, the '*per PT*'-analysis, which is reported in both Tables identically, is preferable.

Comparing EAIRs between the analyses outlined below on a SOC-specific or a global level demonstrates that the '*per PT*'- method makes the interpretation of results more difficult. However, it can be suggested that this method provides a more robust approach when the two treatment arms are to be compared on a SOC-specific or global level. A t-Test like comparison of PT-specific estimates between the two treatment arms may provide a more robust, comprehensive and easy-to-communicate way of visualizing and comparing results.

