## **4.4. Extent of Exposure**

Extent of exposure to study drug will be summarized and presented on safety analysis set.

Treatment duration and the total number of treatment cycles will be summarized descriptively. The number and percentage of subjects treated within each cycle will also be summarized for the dara-SC subjects.

Treatment duration in months is derived as last non-zero daratumumab dosing date – first non-zero daratumumab dosing date + 1 and then divided by 365.25/12. The maximum number of treatment cycles for each subject is the largest cycle number in which a subject receives any non-zero dose of daratumumab.

Total dose (mg) for Dara group is defined as the sum of total dose (mg) administered and recorded on CRF at each visit. Descriptive statistics for the total daratumumab dose received and total number of injections will be provided.

Dose intensity, which is defined as the sum of total dose administered in all cycles divided by the number of treatment cycles, will be calculated and summarized for daratumumab treatment

group. Additionally, the daratumumab dose intensity will be summarized by Cycle during the treatment.

Relative dose intensity (%), which is defined as the ratio of total dose received and total planned dose (calculated as the planned dose level times the number of administered injections), will be calculated and summarized for each treatment group. Additionally, the relative dose intensity will be summarized by Cycle during the treatment.

The incidences of dose delays and corresponding reasons will be provided. The frequencies of actions planned prior to injection start and taken during injection will be summarized, together with reasons reported on eCRF. In addition, a summary of dose delays will also be provided by cycle during the treatment.

The treatment label identifier dispensed by each subject will be listed.

A separate listing including all daratumumab injection data will also be provided.

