### **5. EFFICACY**

#### **5.1. Analysis Specifications**

##### **5.1.1. Level of Significance**

All hypotheses testing will be conducted at a 2-sided level of significance of 0.05. When required, 95% confidence intervals will be constructed.

The primary hypothesis is to be tested at the 0.05 significance level. If the primary endpoint of PFS is statistically significant at the primary analysis, the following secondary endpoints ordered below will be sequentially tested, each with an overall two-sided alpha of 0.05, by utilizing a hierarchical testing approach as proposed by Tang and Geller (1999) that strongly controls Type I error rate:

- ORR
- PFS2
- OS

If the null hypothesis for any of the endpoints fails to be rejected at the primary analysis time point, then any of the subsequent endpoint(s) listed above will not be tested until the next analysis timepoint, if applicable. If the null hypothesis for an endpoint is rejected at a analysis time point, it will remain being rejected and will not be re-tested at the next analysis timepoint, if any. The significance level for each of the above secondary endpoints will be determined by the alpha-spending function specific to the endpoint. The ORR will only be tested at the primary analysis time point with a 2-sided level of significance of 0.05. For PFS2, and OS, alpha spending at the primary analysis time point and the final analysis point will be determined by a linear alpha spending function based on the observed number of the events at the time, i.e., the cumulative alpha to be spent will be the total alpha (0.05) multiplied by the proportion of the observed number of the events out of the total expected number of the events. For example, if 59% targeted PFS2 events are observed at the primary analysis, the corresponding alpha level will be 0.0295(2-sided)). A total of 134 PFS2 events and a total 107 OS events are expected at the final analysis.

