### 2.2. Duration of exposure: censored & non-censored

The incidence rate for a patient is derived from the duration of exposure to treatment of that patient. When averaging incidence rates, a patient's duration of exposure is given either A) by the time when the event has occurred (non-censored data), or B) by the total duration of treatment in case the patient does not show the adverse event in question (censored data). Depending on whether a patient has an adverse event or not, the duration of exposure enters the denominator in its non-censored or censored form, respectively.

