## 2.5. EAIRs on the level of a SOC and on the global level on a 'per-PT' basis

### 2.5.1. Average EAIR per PT

The  $EAIR$  for a specific PT is an average over all patients, i.e.

$$EAIR_{PT} = \frac{\sum_{i=1}^n TEAE_{PT,i}}{\sum_{i=1}^n t_{PT,i}},$$

whereby the number of TEAEs and durations of exposure enter the nominator and the denominator.

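### The SAP's suggested t-test across preferred-term incidence rates has the wrong unit of replication, and the rates have no defined person-time in Arm A

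*SAP*

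**What the plan says.** SAP Attachment 1 is titled "ADDITIONAL EXPLORATORY ANALYSIS TO SUPPORT HEMAR". Its section 2 defines exposure-adjusted incidence rates (EAIRs) of treatment-emergent adverse events. Section 2.5.1 states that the EAIR "for a specific PT is an average over all patients", that is, first events of that term divided by summed exposure. Section 2.1 then suggests: "A t-Test like comparison of PT-specific estimates between the two treatment arms may provide a more robust, comprehensive and easy-to-communicate way" of displaying and comparing results. It does not say whether the test is paired by term, on which scale it is run, which terms enter, or at what level.

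On dependence, section 2.1 says: "The analysis restricts on the first event of a patient because independence of TEAEs cannot be assumed". Its reason is that "patients suffering from infections may have in general a higher risk of having other complications".

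On the denominator, section 2.2 gives a subject's exposure as the time of the event or, failing that, "by the total duration of treatment in case the patient does not show the adverse event in question (censored data"). Section 2.4 repeats this. The only definition of treatment duration is in SAP 4.4: "Treatment duration in months is derived as last non-zero daratumumab dosing date" minus the first such date plus 1. SAP 6.1 counts Arm B events through 30 days after the last dose (or until the day before subsequent therapy), and gives Arm A a separate window that starts at randomization.

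**The concern.** A t-test across terms takes the preferred term as its sample unit, so its standard error reflects only term-to-term scatter. Randomization acts on subjects. If one arm happens to contain more event-prone subjects, many term rates in that arm rise together, and the test reads this as repeated independent evidence. Counting only the first event removes repeats within a term. It does nothing about dependence between terms, which is the dependence that section 2.1 describes.

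At stake is an exploratory between-arm safety statement. It could report a difference that is chance, or miss a real one, depending on a choice the SAP leaves open. The denominator gap matters for every EAIR, whatever test is used: the rate cannot be computed for Arm A as written.

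**Working it through.** **No figure to reproduce.** The documents give no error rate, frailty variance, number of terms or event rate for this comparison. The inputs from the SAP are 180 subjects per arm (1.4) and a 36-month phase (1.2). A two-sided 0.05 level is assumed: SAP 5.1.1 says "All hypotheses testing will be conducted at a 2-sided level of significance of 0.05", but in the efficacy section. The rest is assumed and varied.

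**Why pairing inflates the error.** Give each subject a frailty with mean 1 and variance θ that multiplies all of that subject's term rates. The arm difference in mean frailty then has SD √(2θ/180). For θ = 0.5 this is √(1/180) = 0.075; for θ = 2 it is √(4/180) = 0.149. All terms shift together by about 7-15% by chance, and a paired test across terms does not count this variation.

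**Why not pairing deflates it.** With a log-SD of 1 for term rates, the coefficient of variation is √(e − 1) = 1.31. For 100 terms the standard error of the difference, relative to the mean rate, is at least 1.31 × √(2/100) = 0.185. Significance needs a difference of about 1.97 × 0.185 = 0.37 of the mean rate, far beyond chance shifts of about 0.075, and equally hard for a real effect to reach.

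**Null simulation.** Identical term rates in both arms; gamma frailty; 30% early censoring; 8 expected events per subject; log-SD of term rates 1; 600 replicates per cell. Ranges are over 30, 100 and 300 terms.

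| θ | Paired | Paired, log rates | Unpaired (Welch) | Subject as unit |
|---|---|---|---|---|
| 0 | 3.0-5.7% | 2.8-5.3% | 0% | 3.8-5.2% |
| 0.25 | 16.2-25.8% | 12.3-16.0% | 0-0.2% | 4.2-5.8% |
| 0.5 | 27.8-35.2% | 18.2-27.0% | 0-2.5% | 3.7-5.3% |
| 1 | 38.0-48.3% | 27.7-37.2% | 0-7.5% | 4.3-5.5% |
| 2 | 48.3-60.5% | 39.2-51.3% | 0.5-20.7% | 3.5-5.5% |

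The subject-level test is a Welch test on the number of distinct terms per subject.

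**Sensitivity.**
- 100 terms, expected events 4-15, log-SD 0-1.5 (500 replicates): paired 17-48% at θ = 0.5 and 31-60% at θ = 1; subject-level 3.4-6.8%.
- All terms with the same rate: the unpaired test also rejects 25-60%.
- Correlation only within 20 SOCs (variance 0.5, no overall frailty): paired 6.0%.
- Median term rate 0.0015 per month, log-SD 1.2, follow-up 12-36 months, θ = 0.3-1.0 (300 replicates): paired 32-52% with 150 terms and 51-71% with 400 terms. The 400-term case implies about 25 distinct terms per subject.
- 50-400 terms: paired 19-69% at θ = 0.3-1.0, and 6-32% at θ = 0.1.

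**Denominator.** Arm A receives no daratumumab, so the SAP 4.4 formula has no dates to use. In Arm B, a subject who completes 39 cycles has a last dose at day 38 × 28 + 1 = 1065, with events counted to day 1095. If event-free, that subject loses 30/1095 = 2.7% of the time at risk. A subject who stops after Cycle 2 Day 22 (day 50) loses 30/80 = 37.5%, if no subsequent therapy starts in that time. The numerator covers time that the denominator omits, so Arm B rates are biased upward.

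**The case against.** The sentence is tentative, concerns display as well as comparison, and sets no hypothesis, level or decision rule. The sentence before it, on SOC-level and global comparison, concerns the per-term averaging method and not the t-test. The main safety summaries in SAP section 6 do not use it. The same attachment already plans subject-based work: first-event rates per SOC and overall with one exposure time per subject (section 2.6), and hazard ratios with Kaplan-Meier curves for overall categories and common terms (section 3, on time-to-event analyses). All of this stands, and it limits the importance of the point.

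Two stronger readings are tempting. A reader might infer that the test has one known false-positive rate, for example 30-70%. The documents do not support that: they specify neither pairing nor the inputs, and the unpaired form usually errs in the other direction. A reader might also infer that the question whether events arise faster on daratumumab goes unanswered. It does not, given the planned hazard-ratio analyses.

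The objection does not rescue the sentence itself. The later sections neither withdraw it nor define person-time, and the time-to-event section plans no comparison by SOC. The 30-day omission is small for completers, but the Arm A gap is complete.

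**Conclusion.** The point holds as a defect of an optional, exploratory analysis. The wrong unit of replication follows from the SAP's own text and needs no simulation. Its size does rest on assumptions: roughly 15-60% false positives if paired on raw rates with subject-frailty variance of about 0.25-2, near nominal if correlation lies only within SOCs, and about 70% at the extreme of 400 terms. If unpaired with unequal term rates, rejection is usually far below 5%, with exceptions at high frailty and many terms (up to about 21%). A subject-level test stayed at 3-7% throughout. The denominator defect is textual and independent of these assumptions. Neither affects a primary conclusion.

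**What to change.** 1. Delete the t-test sentence in Attachment 1, section 2.1, or state that the per-term display is descriptive only.
2. Base between-arm statements on the subject. Use the hazard-ratio and Kaplan-Meier analyses already planned in the attachment, and add rate ratios with confidence intervals to the first-event rates of section 2.6 (for example Poisson with a log person-time offset). Where terms are combined, resample subjects in a bootstrap.
3. Replace treatment duration in sections 2.2 and 2.4 with the at-risk window of SAP 6.1 in both arms. State how related events that begin after the Arm B window, which SAP 6.1 also counts, enter the rate.

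The cost is about a paragraph of the attachment and standard code. No new data are needed.
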